9.4 Data Sources

The data collected for a participant will be those that exist in their medical records as part of standard medical care. No additional procedures or activities are required in this registry except for QoL assessments and post-treatment safety follow-up in the context of fulfilling the Specific Obligation (SO2).

Definitions of source data and source documents are provided in Section 9.8.3.

9.5 Study Size

The objective is to screen all Increlex®-treated patients with SPIGFD at each site of the participating countries with the aim of enrolling as many patients as possible.

9.6 Data Management

Data management will be conducted by a SP directed by the Sponsor's Clinical Data Group Leader. All data management procedures will be completed in accordance with the SOPs of the Sponsor and the contracted SP.

9.6.1 Data Collection

The specific data to be collected at each visit are summarised in the Schedule of Assessments (Table 1).

Data will be collected in an eCRF via the internet utilising a secured website. The Sponsor and the SP will ensure that the eCRF developed is appropriate to capture the data required by the protocol. The Sponsor will ensure that the entrusted SP uses adequate technology to ensure data security transfer and backup.

Each site is required to have a computer and internet connection available for site entry of clinical data. Data entry in the eCRF will be performed by the Investigator or by the designated person from his/her team and in order to ensure confidentiality and security of the data, all entries into the eCRF will be made under the electronic signature (e-signature) of the person performing the action (username and password). Only Sponsor-authorised users will be given access to the eCRF as appropriate for their study responsibilities. All users must have successfully undergone software application training prior to entering data into the eCRF.

Once written informed consent has been obtained, the eCRF will provide a numeric participant identifier to pseudonymise the data from each participant. Data for each participant must be entered into the eCRF within 5 days of the participant's enrolment. The data in the eCRF will be transmitted to the Sponsor for analysis. Data transmitted will be pseudonymised and will be identified only by the participant number. Only investigating sites will be able to link the numeric identifier to each participant's identity.

In compliance with GPP, the participant's medical records should be clearly marked and permit easy identification of their participation in this study.

Medical history and AE terms will be coded using the Medical Dictionary for Regulatory Activities (MedDRA) by the contracted SP and reviewed by the Sponsor.

Queries will be edited in English and addressed to the investigational site using the eCRF. Investigators or authorised registry staff members will answer the queries directly into the eCRF.

The eCRF will be signed electronically to certify that all the data recorded in it are consistent with the source documents and reflect the status of the participant during the corresponding part of the registry.

9.6.2 Data Archiving and Retention

During the initiation visits, the monitor must ensure that the archiving facilities are adequate and archiving/retention responsibilities of the Investigator have been discussed.

Registry documents should be retained for at least 15 years after registry completion. However, these documents should be retained for a longer period if required by the applicable regulatory requirements or by agreement with the Sponsor. The Investigator should take measures to prevent accidental or premature destruction of these documents. The final archiving arrangements will be confirmed by the monitor when closing-out the site. The Sponsor will inform the Investigator, in writing, as to when these documents no longer need to be retained.

If the Principal Investigator relocates or retires, or otherwise withdraws his/her responsibility for maintenance and retention of registry documents, the Sponsor must be notified (preferably in writing) so that adequate provision can be made for their future maintenance and retention.

9.7 Data Analysis

9.7.1 Analyses Population Definitions

At the site level:

Screened: site which has been contacted for participation in the registry and confirmed that they are currently following patients who may be eligible for the registry (this includes both participating and non-participating sites).

Participating: site which has agreed to participate in the registry and has completed a patient screening log (as minimum data requested for participation).

At the patient/participant level:

Screened Population: all patients included in the patient screening log (this includes both enrolled and non-enrolled patients, with the reason for non-enrolment).

Enrolled Population: all participants who are fully informed about the registry and who have given their written informed consent to participate (and/or their parents/legally authorised representatives) before implementation of any registry-related procedure.

Registry Population: all participants who have completed at least one follow-up visit and who have taken the treatment at least once.

Complete Population: all participants who have stopped treatment and who have been followed until FAH reached.

Safety Population: all participants who have taken the treatment at least once and with at least one follow-up visit or presence of any post-study treatment safety data.

Long-term Safety Population: all participants who have been exposed to Increlex® for at least 3 years and who ended therapy at least 2 years prior to the collection of long-term safety data. The primary analysis based on the primary endpoint will be performed on the Safety Population.

9.7.2 *Statistical and Analytical Methods*

9.7.2.1 *Statistical Analyses*

The statistical analyses will be performed by an external SP managed by the Sponsor.

A Statistical Analysis Plan (SAP) describing the planned statistical analysis in detail with tables, figures and listings templates will be developed as a separate document.

Statistical evaluation will be performed using Statistical Analysis System (SAS)[®] (Version 9 or higher).

As this is a non-interventional study, no formal statistical testing will be performed and all the analyses will be primarily descriptive in nature. When appropriate and unless otherwise specified, 2-sided 95% confidence intervals (CIs) will be displayed and if p-values are presented, they will be for exploratory purposes only.

Descriptive statistics will include number of available data, number of missing data and the following:

- Mean, SD, 95% CIs for means when appropriate, median, quartile, minimum and maximum for continuous variables;
- Frequency count, percentages and 95% CIs when appropriate for categorical nominal variables;
- Both the above for categorical ordinal variables.

Missing data will not be replaced but they will be displayed in all relevant tables.

9.7.2.2 *Participant Inclusion*

Based on the screened population, the proportion of non-included patients will be assessed as well as the reasons for non-inclusion.

9.7.2.3 *Demographic and Other Baseline Characteristics*

Descriptive statistics of demographic and baseline data will be presented for the Registry Population.

Previous/concomitant medications will be summarised by drug categories.

Data on medical history, coded using MedDRA, and previous growth therapy will be summarised.

Information on SPIGFD diagnosis, personal or familial risk factors for neoplasia and genetic test results (deletion/mutation of GH gene, IGF-1 gene, FGF, PTPN11, GHR, D3-GHR, STAT5b, ALS, SHOX, PAPPA2 and any other genetic tests performed, e.g. whole exon sequencing) will be described.

9.7.2.4 *Participant Disposition and Withdrawals*

The numbers and percentages of participants included in the analysis populations will be tabulated overall and by country and site. The reasons for participant exclusions from each of the populations will also be tabulated.

In addition, the number of participants who ended the treatment, withdrew or completed the registry will be presented with the primary reasons for discontinuation.

9.7.2.5 *Primary Analyses*

The primary analyses and summary tables of safety data will be based on the Safety Population (data from the treatment period only).

An overall summary table of AEs during the treatment period (up to 30 days after the last dose) including SAEs, AESI, targeted AEs, all AEs, AEs leading to death and AEs leading to withdrawal will be presented with the number and proportion of participants and the number of events.

All treatment emergent AEs (TEAEs) will be coded according to MedDRA and will be classified by MedDRA primary system organ class (SOC) and preferred term (PT). The incidence of all TEAEs, SAEs, AESI, targeted AEs, AEs leading to death and AEs leading to withdrawal will be tabulated by primary SOC and PT. In addition, summary tables by maximum intensity and drug relationship will be presented.

AE listings will be presented by participant, primary SOC and PT.

The relationship of frequently occurring AEs, e.g. hypoglycaemia, to prognostic variables such as age, pubertal status, and dose will be explored.

All primary safety data will also be included in the participant data listings.

9.7.2.6 *Secondary Analyses*

Safety Analyses

The secondary safety analyses will be based on the Safety Population. Adverse event data are from the post-treatment period only but data on special situations and concomitant medications are from the treatment and post-treatment periods.

An overall summary table of AEs occurring during the post-treatment period (over 30 days after the last dose) including SAEs, AESI, targeted AEs, all AEs and AEs leading to death will be presented with the number and proportion of participants and the number of events.

The incidence of all post-treatment AEs, SAEs, AESI, targeted AEs and AEs leading to death will be tabulated by MedDRA primary SOC and PT. In addition, summary tables by maximum intensity and drug relationship will be presented.

The same analyses will be performed in a subset of children and adolescents exposed to Increlex® for at least 3 years.

Post-treatment AE listings will be presented by participant, primary SOC and PT.

An overall summary table of special situations occurring during the treatment and post-treatment periods will be presented with the number and proportion of participants and the number of events. For the post-treatment period, the same analyses will be performed in a subset of children and adolescents exposed to Increlex® for at least 3 years.

Concomitant medications during the treatment and post-treatment periods will be tabulated.

Incidence of neoplasia (benign and malignant) and hypoglycaemia will be presented according to the timeframe of occurrence (e.g. within the first 3 years after start of treatment, between 3 and 5 years and over 5 years).

All secondary safety data will also be included in the participant data listings.

Effectiveness Analyses

Effectiveness analyses will be based on the Registry Population.

The raw values of the following effectiveness parameters will be described at different timepoints (every 6 months from the start of treatment) as well as the change from baseline: height SDS, height velocity, BMI SDS, bone age development, pubertal stage.

For participants who reached the FAH, the estimation of the difference between the PAH and the FAH will be presented.

Main effectiveness parameters (height SDS, height velocity) will be described according to average dose received over the course of the study and according to dose ranges (e.g. 4 dose ranges (≤ 50 , $]50-80]$, $]80-110]$, $> 110 \mu\text{g/kg BID}$)). This analysis will support the description of the lowest effective dose.

Multivariate linear regression analyses will be used to identify predictive factors of height SDS change, height velocity, bone age development after 1 year of treatment or more. The same method will be used to assess the predictive factors of FAH.

The Cox regression model including covariates as sex, age or height SDS at start of Increlex® will be used to estimate the time from start of treatment to reach the puberty for a subset of prepubertal patients at start of Increlex®.

Biological assessments (IGF-1, IGFBP3), raw values and change from baseline, will be described at different timepoints.

Exposure to Increlex® Therapy

The treatment duration as well as the dose of Increlex® at each timepoint (initiation, 3 months, 6 months, 1 year, and every 6 months thereafter) will be described.

Duration of post-treatment follow-up will also be summarised.

Quality of Life Analysis

The QoL of participants aged 4 and over will be assessed using the EQ-5D-Y paediatric questionnaire (see Section 9.3.2.5 for details).

The 5 dimensions/domains (mobility; looking after myself; doing usual activities; having pain or discomfort; feeling worried, sad or unhappy) will be described at each timepoint as well as the evolution from baseline. The VAS will be described as a quantitative parameter at each timepoint as well as the change from baseline.

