9.2.1 Inclusion Criteria

(2) Children and adolescents from 2 to 18 years:

- For US, patients starting or planning to start or currently receiving treatment with Increlex® therapy for severe primary IGF-1 deficiency as defined by the US Increlex® prescribing information or for growth hormone (GH) gene deletion who have developed neutralizing antibodies to GH.
- For EU, patients starting or planning to start or currently receiving treatment with Increlex® therapy according to the locally approved product information. Note:

not applicable for patients enrolled in the EU-IGFD registry and entering or currently in the post-treatment period.

(2) Signed informed consent as per local regulations needs to be obtained. Parents or legally authorised representatives if applicable must give signed informed consent before any registry-related activities are conducted. Assent from the participant should also be obtained as appropriate.

9.2.2 *Exclusion Criteria*

(1) Patient currently participating in an Increlex® clinical trial.

(2) Patient currently participating in any clinical trial for growth retardation.

(3) Patient with any contraindication to Increlex® or any condition subject to special warning as per the locally approved label.

- For US patients, these include patients with hypersensitivity to the active substance or any of the excipients, patients with active or suspected neoplasia and patients with closed epiphyses.
- For EU patients: these include patients with hypersensitivity to the active substance or any of the excipients, patients with active or suspected neoplasia or any condition or medical history which increases the risk of benign or malignant neoplasia and patients with closed epiphyses. Note: not applicable for patients enrolled in the EU-IGFD registry and entering or currently in the post-treatment period.

Note: for any patients enrolled in the registry under previous inclusion/exclusion criteria (i.e. before implementation of Protocol Amendment #6), who would be ineligible according to any of the above inclusion or exclusion criteria, e.g. receiving Increlex® for an indication not covered by the locally approved product information, a letter will be sent to the Investigator to alert him/her about the off-label use of the product (specifically for the risk of neoplasias). The patient could continue to be followed up in the registry for safety data in the post-treatment period.

9.2.3 *Registry Population*

9.2.3.1 *Physician Profile*

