 - Antibiotics, medication for attention deficit disorder, anti-depression medication, aromatase inhibitors, gonadotrophin releasing hormone agonists, thyroid hormone, GH, androgens, oestrogens, glucocorticoids, bronchodilators, other psychiatric medications and other chronic medications
- IGF-1 concentrations (unit of measure, level, date acquired, name of assay) including both absolute value and SD or percentile of assay-specific reference, if references available
- Serum IGFBP3 (serum level in ng/ml and name of assay)
- Bone age and method (e.g. GP method) and date of X-ray, echocardiogram and funduscopy
- Physical examination including:
 - Current height, sitting height and weight measurements and FAH (if available)
 - Pubertal (Tanner) stage: pubic hair, testicular volume, breast development
- Increlex® therapy: all doses changes (including interruptions) with posology, dates and reasons for change will be collected. For drug compliance, number of missing doses will also be collected
- All AEs, including SAEs, AESI and targeted AEs (see Section 11.1.5), and special situations. Onset and recurrence of benign and malignant neoplasias will be considered as AESI and should also be reported as SAE
 - For hypoglycaemia (documented or suspected), time from last Increlex® dose to time of event, blood glucose level (if available) and event resolution without intervention other than feeding (Yes/No) should also be collected
- Discontinuation of therapy
 - Date of last dose
 - Reason for discontinuing therapy, the most appropriate response should be selected: attained adult height, AE, lost to follow-up, noncompliance, participant/parent/legally authorised representative decision, financial/insurance, changed physician, lack of effectiveness, shortage of Increlex®, physician decision, COVID-19 or other (if other the reason should be specified)

- QoL assessment using EQ-5D version EQ-5D-Y on participants aged 4 and over at year one, at end of treatment and at FAH (see Section 9.3.2.5).

9.2.7.3 *Post-treatment Visits*

The importance of the follow-up visits, including at least visits at years 2 and 5 after the end of treatment, should be noted. The following data will be recorded:

- Visit date
- Concomitant medications including:

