 - Antibiotics, medication for attention deficit disorder, anti-depression medication, aromatase inhibitors, gonadotrophin releasing hormone agonists, thyroid hormone, GH, androgens, oestrogens, glucocorticoids, bronchodilators, medication for diabetes, medication for high blood pressure, medication for malignancy, medication for hyperlipidaemia, medication for immune system disorders, medication for coagulation disorders, other psychiatric medications and other chronic medications
- IGF-1 concentrations (unit of measure, level, date acquired, name of assay)
- Bone age and method (e.g. GP method) and date of X-ray (in case adult height not reached), echocardiogram and funduscopy
- Physical examination including:
 - Current height, sitting height and weight measurements and FAH (if available)
 - Pubertal (Tanner) stage: pubic hair, testicular volume, breast development
- All AEs, including SAEs, AESI and targeted AEs (see Section 11.1.5), and special situations. Onset and recurrence of benign and malignant neoplasias will be considered as AESI and should also be reported as SAE
 - For hypoglycaemia (documented or suspected), time from last Increlex® dose to time of event, blood glucose level (if available) and event resolution without intervention other than feeding (Yes/No) should also be collected
- QoL assessment using EQ-5D version EQ-5D-Y at FAH (see Section 9.3.2.5).

9.2.8 *Registry Discontinuation/Withdrawal*

The participant will be withdrawn from the registry:

- If informed consent is withdrawn (participant/parent or legally authorised representative decision; the participant must be informed that they may decide to withdraw from the registry at any time without any effect on their treatment and the normal follow-up of the disease);
- At the end of the post-treatment follow-up (5 years after stopping treatment or at adult height if later);
- If the participant is lost to follow-up;
- If the participant is included in a clinical trial for growth retardation.

If a participant is withdrawn from the registry, the date and primary reason for withdrawal should be recorded in the eCRF as well as if the participant stopped Increlex® therapy or not.

Investigators may decide to stop their participation in the registry at any time without consequences on the normal participant follow-up. If this occurs, every effort should be made to transfer care of the participant to a new physician to enable the participant to continue in the registry.

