- Description and evolution of QoL in participants aged 4 and over using EQ-5D version EQ-5D-Y including changes from baseline at year one, at end of treatment and at FAH;
- Description of neoplasia (benign and malignant) and hypoglycaemia according to the timeframe of occurrence (e.g. within the first 3 years after start of treatment, between 3 and 5 years and over 5 years).

9.3.2 *Variables*

9.3.2.1 *Demographic and Baseline Variables*

The registry will collect the following data:

- Demographic data on children and adolescents receiving Increlex® treatment: sex, date of birth (month and year), birth weight and length, gestational age, previous and current height, sitting height and weight;
- Parental heights (biological relatives only);
- Baseline height, sitting height, weight, bone age and method, echocardiogram, funduscopy and pubertal (Tanner) stage;
- Pregnancy status;
- PAH;
- Diagnosis of SPIGFD (documented by height SDS; IGF-1 levels and IGF-1 SDS; GH levels), date of diagnosis and associated aetiologies, and date of growth failure (short stature) diagnosis, if different from SPIGFD diagnosis date;
- IGF-1 generation test results and IGF-1/IGFBP3 concentrations;
- GH concentrations including basal/random and highest stimulated;
- Serum IGFBP3;
- GHBP;
- Genetic test results and date of genetic testing;
- Current and previous illnesses including congenital conditions and neoplasia;
- Previous and concomitant medications;
- Personal and family history of neoplasia;
- Prior growth-promoting therapies: GH, IGF-1, steroid hormones such as sex steroids (testosterone and oestradiol);
- Baseline QoL assessment using EQ-5D version EQ-5D-Y.

9.3.2.2 *Safety Variables (Primary Analyses; Treatment Period and Secondary Analyses; Treatment and Post-treatment Follow-up Periods)*

Data on the following safety variables will be collected from enrolment to the end of the post-treatment follow-up period:

- For all AEs, irrespective of causality, including SAEs, AESI and targeted AEs, start/end date, time to onset, nature, severity, seriousness, causality assessment, any treatment administered for the AE, action taken and outcome;
- Deaths, irrespective of causality, including date and cause of death;
- Special situations, irrespective of causality, including start/end date, category, description, whether the special situation led to an AE and outcome;
- Concomitant medications including concomitant treatment with GH, with start/end dates;

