7.2 Does the protocol address:				
7.2.1. Selection biases (e.g. healthy user bias)				N/A
7.2.2. Information biases (e.g. misclassification of exposure and endpoints, time-related bias)				N/A
7.3 Does the protocol address the validity of the study covariates?				N/A
Comments: Confounding and covariates do not apply to this study.				

Section 8: Effect modification	Yes	No	N/A	Section Number
8.1 Does the protocol address effect modifiers? (e.g. collection of data on known effect modifiers, sub-group analyses, anticipated direction of effect)				N/A
Comments: Effect modifiers are not applicable to this study.				

Section 9: Data sources	Yes	No	N/A	Section Number
9.1 Does the protocol describe the data source(s) used in the study for the ascertainment of:				
9.1.1 Exposure? (e.g. pharmacy dispensing, general practice prescribing, claims data, self-report, face-to-face interview, etc.)				9.4, 9.8.3
9.1.2 Outcomes? (e.g. clinical records, laboratory markers or values, claims data, self-report, subject interview including scales and questionnaires, vital statistics, etc.)				9.4, 9.8.3
9.1.3 Covariates?				N/A
9.2 Does the protocol describe the information available from the data source(s) on:				
9.2.1 Exposure? (e.g. date of dispensing, drug quantity, dose, number of days of supply prescription, daily dosage, prescriber)				9.3, 9.8.3
9.2.2 Outcomes? (e.g. date of occurrence, multiple event, severity measures related to event)				9.3, 9.8.3
9.2.3 Covariates? (e.g. age, sex, clinical and drug use history, co-morbidity, co-medications, lifestyle, etc.)				N/A
9.3 Is a coding system described for:				

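### The time-to-puberty, bone-age and growth analyses state no handling of recorded puberty- and growth-modifying co-medication, while the checklist says confounding and covariates do not apply

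*Protocol*

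**What the plan says.** **Model and descriptions.** Section 9.7.2.6 (Effectiveness Analyses) plans a Cox model: "The Cox regression model including covariates as sex, age or height SDS at start of Increlex® will be used to estimate the time". The clock runs from the first Increlex dose to puberty, and the model is confined to children who had not entered puberty by then. The covariates it names are all start-of-treatment characteristics. The same section describes height SDS, height velocity, BMI SDS, bone age and pubertal stage every 6 months, presents the difference between predicted and final adult height (PAH and FAH), and plans multivariate linear regressions for growth, bone age and FAH without listing predictors. All of this is on the Registry Population, with no condition on co-treatment.

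**Co-medication.** The exclusion criteria (9.2.2) cover contraindications, label warnings and trial participation, for example "Patient currently participating in any clinical trial for growth retardation". No puberty- or growth-modifying drug is excluded. The visit forms name them. The follow-up list (9.2.7.2) includes "aromatase inhibitors, gonadotrophin releasing hormone agonists, thyroid hormone, GH, androgens, oestrogens, glucocorticoids, bronchodilators", and the enrolment list (9.2.7.1) and post-treatment list (9.2.7.3) name the same classes. Section 9.3.2.2 collects "Concomitant medications including concomitant treatment with GH, with start/end dates". Baseline history (9.3.2.1) covers "Prior growth-promoting therapies: GH, IGF-1, steroid hormones such as sex steroids (testosterone and oestradiol". The only stated use of these data is summary or tabulation (9.7.2.3, 9.7.2.6, 9.7.3).

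**Checklist.** In Appendix 2, the comment to Section 7 (Bias) reads "Confounding and covariates do not apply to this study". The comments to Sections 9 and 12 repeat this for covariates and for confounding respectively, and item 10.4 marks adjustment for confounding as not applicable.

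**The concern.** Timing and progression of puberty and bone-age development are named in the secondary objectives (8.2.2), together with height velocity, height SDS change and FAH. Several recorded drug classes act directly on these outcomes. By general pharmacology, which the protocol does not discuss, a GnRH agonist suppresses puberty, androgens and oestrogens can produce pubertal signs, and aromatase inhibitors and GH can affect bone age or growth. For an exposed child, the puberty date can be the result of a prescription. This goes beyond ordinary confounding, because the co-drug can set the event itself.

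A covariate fixed at Increlex start cannot represent a drug begun later. If nothing further is done, a suppressed child stays in the risk set as though able to enter puberty, and an induced onset may be read as spontaneous. The described time to puberty then has no clear meaning, and the same mixing reaches bone age, pubertal stage, height velocity and FAH minus PAH.

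**Working it through.** **1. Text check.**
- Are the drugs permitted? Yes: 9.2.2 excludes none of them.
- Are they recorded with dates? Yes: 9.2.7.1 to 9.2.7.3 for the classes, 9.3.2.2 for start and end dates.
- Does 9.7.2.6 state a covariate, time-varying term, censoring rule, exclusion or sensitivity analysis for them? No.
- Does 9.7.3 name them as a subgroup? No. It offers previous treatment, among other examples, as optional.
- Is Appendix 2 consistent with 9.7.2.6? No. One says covariates do not apply; the other names covariates for a Cox model and plans multivariate regressions.

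**2. Size.** The protocol gives no prevalence of these drugs, no distribution of puberty onset and no event count. There is no figure to reproduce, and everything below rests on assumed inputs.

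*Illustration A, suppression started at a fixed time.* Assume spontaneous onset T ~ Normal(4, 1.5) years after start. A share p of children still prepubertal at year 3 takes a GnRH agonist, which delays onset by 2 years.
- P(T > 3) = Φ((4 − 3)/1.5) = Φ(0.667) = 0.7475.
- Shift in mean = 2 × p × 0.7475. For p = 10%, 20%, 30% this is 0.15, 0.30, 0.45 years, so the mean goes from 4.00 to 4.15, 4.30, 4.45.
- For t > 5 the observed distribution is (1 − p)Φ((t − 4)/1.5) + pΦ((t − 6)/1.5). Setting it to 0.75 gives a 75th percentile of about 5.26, 5.52, 5.78 years, against 5.01 without the drug.

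*Illustration B, suppression in a random share of all children.* Assume T ~ Normal(5, 2) and a 2-year delay in a share p. The median solves (1 − p)Φ((t − 5)/2) + pΦ((t − 7)/2) = 0.5.

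| Share p | Median, drug unhandled | Kaplan-Meier median, censored at drug start (0.25 year before onset; simulated) |
|---|---|---|
| 0% | 5.00 | – |
| 5% | 5.09 | 5.08 |
| 10% | 5.18 | 5.17 |
| 20% | 5.37 | 5.37 |
| 30% | 5.57 | 5.61 |

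When the drug is started because puberty is imminent, censoring at its start is informative and removes almost none of the shift. Under illustration A, where the start is at a fixed year in a random share, censoring returns the 75th percentile to 5.01. Whether censoring helps therefore depends on why the drug was started.

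*Illustration C, induction.* Assume T ~ Normal(5, 2), with induction at year 6 among those not yet pubertal, amounting to 5, 10, 20 or 30% of all children. By simulation the median stays at 5.0, the mean falls from 5.00 to 4.94, 4.87, 4.74, 4.62, and the 90th percentile falls from 7.55 to 7.34, 7.08, 6.11, 6.00 years.

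The direction of the shift depends on the drug class, and its size on prevalence. At 5% use it is under 0.1 year in the median.

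**The case against.** The strongest reply is that this is SAP content. Section 9.7.2.1 defers detail to a separate SAP that is not shown here, and censoring rules, time-varying terms and co-medication sensitivity analyses usually sit there. The named Cox covariates read as examples, and the linear-regression predictors are not listed. A reader might infer that the protocol has decided to ignore these drugs. The text does not support that; it states no handling, and the SAP could add it.

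Second, a reader might infer that drug-set puberty dates would be credited to Increlex. The text does not say so either. There is no comparator, the analyses are primarily descriptive with exploratory p-values (9.7.2.1), and an all-patient time to puberty in routine care is a legitimate quantity.

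Third, some exposure may predate Increlex: 9.2.7.1 records chronic GnRH agonists and sex steroids at enrolment. A GnRH agonist started after onset is recorded leaves the onset date unchanged. The protocol does not define the puberty event, so it is open whether every induced onset would count. A named category on a form, beside antibiotics and bronchodilators, does not show material use.

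These replies limit the point but do not remove it. The protocol goes beyond silence, because its own checklist says there is no confounding or covariate to handle while 9.7.2.6 fits covariate models. A descriptive time to puberty is still hard to interpret if it mixes two kinds of onset. The reply that the checklist is only a supporting document is fair, and correcting it alone would be clerical.

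**Conclusion.** The point holds in limited form. Section 9.7.2.6 fixes a puberty-timing model and pooled descriptions of maturation and growth without stating how recorded puberty- and growth-modifying drugs are handled, and Appendix 2 contradicts the models by declaring confounding and covariates inapplicable. Puberty timing, bone age and growth results may mix spontaneous and drug-determined outcomes.

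The size is unknown. The shifts of roughly 0.1 to 0.6 year in the median for suppression in 5 to 30% of children rest wholly on assumed onset distributions, delays and shares. They show that the effect is small at low use and grows with use; they do not estimate this registry's bias. This affects secondary, descriptive objectives and leaves the primary safety analysis untouched. It is a worthwhile, inexpensive improvement, since the data are already collected.

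**What to change.** In 9.7.2.6:

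- **(a) Time to puberty.** Keep the all-patient result. Beside it, report spontaneous and drug-induced onset separately, with induced onset as a competing event and suppressive drugs as a time-varying indicator. Show censoring at drug start only as a sensitivity analysis, because it may be informative.
- **(b) Maturation and growth.** Beside the all-data results, show bone age, pubertal stage and height velocity restricted to time before any GH, GnRH agonist, aromatase inhibitor or sex steroid. FAH is a single terminal value and cannot be cut at drug start, so show FAH minus PAH by ever/never exposure and note that this split is selective.
- **(c) Checklist.** In Appendix 2, correct the comments to Sections 7, 9 and 12 that confounding or covariates do not apply, with the matching not-applicable entries.

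Cost: a little more analysis, and fewer events and child-years in the restricted results. No new data item is needed, because the drug classes and their start and end dates are already collected.
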